3.1.1.1 Rules for DLT Evaluation in Phase 1b

A Dose Level Review Team (DLRT) will review the safety data to evaluate DLT. This team will recommend either to enroll more subjects for DLT evaluation in phase 1b, to prematurely stop enrollment into phase 1b, or to declare that the combination is tolerable based on the criteria described in [Table 1](#) below.

The DLT evaluation period is 6 weeks from the initial administration of study treatment. To be evaluable for a DLT, subjects must have had the opportunity to be on treatment for at least 6 weeks from the initial dosing of study treatment and have received at least 2 doses of talimogene laherparepvec and 2 doses of pembrolizumab in combination, or

have a DLT during the DLT evaluation period after at least 1 dose of talimogene laherparepvec and pembrolizumab in combination. Subjects may be replaced if they are not evaluable for DLT to obtain 18 DLT-evaluable subjects (eg, a subject did not receive study treatment, or ended the study treatment before completion of DLT evaluation period for a reason other than experiencing a DLT).

Safety will be evaluated considering the incidence of DLTs among all DLT-evaluable subjects enrolled in the phase 1b. A sequential stopping rule is derived based on a hypothesis testing approach considering only the first 18 DLT-evaluable subjects (Goldman, 1987). There will be up to 3 planned safety interim analyses. The cumulative increments of DLT-evaluable subjects and corresponding acceptable maximum number and percentage of DLTs at each analysis are indicated in Table 1. The combination will not be declared safe if the number of DLTs exceeds the acceptable maximum number and phase 1b will stop.

Table 1. Cumulative Increments of DLT-evaluable Subjects and Corresponding Acceptable Maximum Number and Percentage of DLTs at Each Planned Interim Safety Analysis

Analysis	Number DLT Evaluable Subjects	Number DLT Evaluable	Acceptable Maximum Number (%) of DLTs
#1	First 4 to 6	4	2 (50)
		5	2 (40)
		6	2 (33)
		7 ¹	2 (29)
#2	4 to 6 new after Analysis #1	8	2 (25)
		9	3 (33)
		10	3 (30)
		11	3 (27)
		12	3 (25)
		13 ¹	3 (23)
#3	Exactly 18 total	18 ²	4 (22)

DLT = dose limiting toxicity

The design achieves a 7.7% 1-sided significance level and 81.6% power to test the null hypothesis of a DLT rate $\leq 10\%$ versus the alternative hypothesis of a rate $\geq 33\%$.

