¹ Although the target is 4 to 6 DLT-evaluable subjects at Analysis #1, and 4 to 6 new subjects at Analysis #2, all DLT-evaluable subjects will be included in each analysis.

² If > 18 subjects receive the combination they will contribute to the overall safety analysis, but only the first 18 DLT-evaluable will be considered in the decision to declare the combination safe.

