10.2 Sample Size Considerations

10.2.1 Sample Size Considerations for Phase 1b

In testing for the null hypothesis H_0 that the combination of talimogene laherparepvec and pembrolizumab has a DLT rate $\leq 10\%$ versus the alternative hypothesis (H_a) that the true DLT rate is $\geq 33\%$, the sample size goal is to have $\geq 80\%$ power for a 1-sided $\leq 10\%$ significance level test to reject H_0 when H_a is true ([Goldman AI, 1987](#)).

With up to 3 safety interim analyses, the sequential stopping rules shown in [Table 1 \(Section 3.1.1\)](#) gives 81.6% power for a 7.7% 1-sided significance level test. A maximum of 18 DLT-evaluable subjects will be enrolled. If > 18 subjects receive the combination they will contribute to the overall safety analysis, but only the first 18 DLT-evaluable will be considered in the decision to declare the combination safe. Subjects may be replaced if they are not evaluable for DLT to obtain 18 DLT-evaluable subjects (eg, a subject did not receive study treatment, or ended the study treatment before completion of DLT evaluation period for a reason other than experiencing a DLT). The null hypothesis may be accepted and the combination declared safe prior to 18 DLT-evaluable subjects if it can be definitively determined that the stopping rule will not be exceeded with additional subjects.

An expansion cohort of up to an additional 22 treated subjects will be enrolled so there will be 40 treated subjects in total. The decision to proceed to phase 3 will consider safety data in all treated subjects and efficacy among all treated subjects excluding those with locoregionally advanced disease with disease progression or recurrence < 3 months after prior platinum-containing curatively intended multimodal therapy. The efficacy analysis is expected to include approximately 27 subjects. The decision to proceed to phase 3 will consider, for example, long-term tolerability and minimum efficacy consistent with pembrolizumab monotherapy historical data.

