3.2 Sample Size

3.2.1 Sample Size Considerations for Phase 1b

See protocol Section 10.2.1.

4. Study Endpoints and Covariates

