8.1.1 DLT Safety Analysis (Phase 1b)

Up to 3 planned safety interim analyses will occur during the phase 1b to evaluate the incidence of DLT according to timing/rules described in protocol Table 1 (Section 3.1.1). At each interim analysis, a DLT listing will be generated. The number and percentage of subjects with DLTs will be tabulated in a summary table among DLT-evaluable subjects. DLT evaluations will be based on the DLT Analysis Set. Data will be reviewed by a DLRT.

9. Data Screening and Acceptance

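### The 7.7% significance level and 81.6% power stated for the DLT stopping rule are not those of the three-look rule in Table 1, which misses the 80% power goal at every targeted schedule at a 33% DLT rate

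*Protocol*

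**What the plan says.** Protocol Section 3.1.1.1 sets a sequential rule for the first 18 DLT-evaluable subjects: "There will be up to 3 planned safety interim analyses". Table 1 gives the largest acceptable number of DLTs at each look: 2 for 4 to 8 subjects, 3 for 9 to 13, and 4 at 18. Phase 1b stops if the number is exceeded. The first look is planned at 4 to 6 subjects, the second after 4 to 6 more, and the third at exactly 18. Footnote 1 explains the off-target rows at 7 and 13: "Although the target is 4 to 6 DLT-evaluable subjects at Analysis #1, and 4 to 6 new subjects at Analysis #2", everyone evaluable at the time is counted.

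Below the table stands: "The design achieves a 7.7% 1-sided significance level and 81.6% power to test the null hypothesis" of a DLT rate of at most 10% against a rate of at least 33%.

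Section 10.2.1 sets the goal of at least 80% power at a 1-sided level of at most 10%. It says that the Table 1 rule, "With up to 3 safety interim analyses", "gives 81.6% power for a 7.7% 1-sided significance level test".

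The SAP keeps the same schedule in Section 8.1.1 ("Up to 3 planned safety interim analyses will occur during the phase 1b to evaluate the incidence of DLT") and takes its sample size basis from the protocol in Section 3.2.1 ("See protocol Section 10.2.1").

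**The concern.** Both protocol sections attach 7.7% and 81.6% to the three-look rule of Table 1. Every input needed to check the pair is printed, and the pair does not follow from them.

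DLT incidence is the phase 1b primary endpoint, and this rule decides whether the combination is declared safe. Here power is the chance of stopping when the DLT rate is 33%. An overstated power therefore overstates the protection that the rule gives, and it hides that the plan's own 80% goal is not met at the planned looks.

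**Working it through.** **Inputs.** Null rate 0.10, alternative rate 0.33, limits 2 (n = 4 to 8), 3 (n = 9 to 13) and 4 (n = 18), stop when the count exceeds the limit: all from Section 3.1.1.1 and Table 1. Assumption: subjects are independent with a common DLT probability p.

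**Formula.** Let X(n) be the DLT count among the first n subjects and m(n) the limit. For looks n1 < n2 < 18,

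P(stop) = P[X(n1) > m(n1)] + P[not stopped at n1, X(n2) > m(n2)] + P[not stopped at n1 or n2, X(18) > 4].

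Each term is an exact binomial sum over the paths that have not yet stopped. At p = 0.10 the total is the significance level, and at p = 0.33 it is the power. Section 10.2.1 also allows safety to be declared early once the limits can no longer be exceeded. That leaves these probabilities unchanged, because the outcome is then already certain.

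**Attempt to reproduce 7.7% and 81.6%.** The first term for a look at 4 is 4p³(1−p) + p⁴:
- p = 0.10: 0.0036 + 0.0001 = 0.00370
- p = 0.33: 0.09631 + 0.01186 = 0.10817

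The two targeted schedules at the extremes are then:
- 4/8/18: level 0.00370 + 0.03439 + 0.01604 = 0.0541; power 0.10817 + 0.41539 + 0.26859 = 0.792
- 4/9/18: level 0.00370 + 0.00676 + 0.02227 = 0.0327; power 0.10817 + 0.24635 + 0.41264 = 0.767

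All schedules with 4 to 6 new subjects at the second look:

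| Looks | Level | Power at 0.33 | Power at 1/3 |
|---|---|---|---|
| 4/8/18 | 5.41% | 79.2% | 80.0% |
| 4/9/18 | 3.27% | 76.7% | 77.6% |
| 4/10/18 | 3.46% | 77.1% | 77.9% |
| 5/9/18 | 3.52% | 77.0% | 77.9% |
| 5/10/18 | 3.69% | 77.3% | 78.2% |
| 5/11/18 | 3.94% | 77.8% | 78.7% |
| 6/10/18 | 4.08% | 77.8% | 78.6% |
| 6/11/18 | 4.31% | 78.2% | 79.0% |
| 6/12/18 | 4.64% | 78.8% | 79.7% |
| 7/11/18 (off target) | 4.86% | 78.8% | 79.6% |
| 7/12/18 (off target) | 5.15% | 79.4% | 80.2% |
| 7/13/18 (off target) | 5.58% | 80.2% | 81.0% |

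Taking all 24 pairs of tabulated sizes (n1 = 4 to 7, n2 = 8 to 13) gives the same outer limits: level 3.27% to 5.58%, power 76.7% to 80.2%. At 0.33 only 7/13/18 reaches 80%.

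**Can look timing close the gap?** A DLT count never falls. Checking a limit after every subject is therefore the same as checking it once, at the last n where it applies. Checking Table 1's limits after every subject from the fourth on equals looks at 8/13/18 (limit 4 assumed for n = 14 to 17). This is the ceiling for any set of looks from n = 4:
- level 0.03809 + 0.01559 + 0.00880 = 0.0625
- power 0.52356 + 0.18144 + 0.10305 = 0.808

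So neither 7.7% nor 81.6% is reached at the printed rates.

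**What does give the stated pair.** Add a look at n = 3 with a maximum of 1 DLT. Its first term is 3p²(1−p) + p³:
- p = 0.10: 0.027 + 0.001 = 0.02800
- p = 0.33: 0.21889 + 0.03594 = 0.25483

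Looks at 3/8/13/18 then give:
- level 0.02800 + 0.02604 + 0.01430 + 0.00829 = 0.0766
- power 0.25483 + 0.29829 + 0.16571 + 0.09700 = 0.8158

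These round to 7.7% and 81.6%. The same values come from monitoring after every subject with a limit of 1 up to n = 3. An extra look at n = 2 instead gives 6.7% and 81.1%, which does not match. Table 1 has no look before 4 subjects.

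**The case against.** Four points can be made for the plan.

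- **33% may mean 1/3.** At 1/3, checking Table 1's limits after every subject gives 81.6% power, which is the stated figure, and the targeted schedule 4/8/18 just reaches 80.03%. This is true, but the documents print 33%, and monitoring every subject is not the planned schedule. The significance level does not depend on the alternative, so it stays at 6.2% at most and 7.7% is still not attained. Over the 12 schedules above, power at 1/3 is 77.6% to 81.0%; only 4/8, 7/12 and 7/13 reach 80%.
- **The figures may be right for a parent boundary.** Section 3.1.1.1 says that the rule was derived from a cited sequential method, and the match with the added limit at n = 3 supports this. But the protocol states the pair for the up-to-three-look design, names no other boundary, and gives no limit below 4 subjects. That the parent boundary is the source remains an inference, and the conclusion does not need it.
- **The shortfall is small.** It is 0.8 to 3.3 points below 80% on the targeted schedules, 33% is the lower edge of the alternative, and the goal for the significance level is met. All of this stands and limits the size of the point.
- **Little depends on it now.** SAP Section 11 records that phase 3 will not go ahead, and no analysis uses the two figures. That also stands. But SAP Section 1 says that the CSR will rest on the phase 1b analyses, and it should not describe the primary-endpoint rule by properties that the rule does not have.

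**Conclusion.** The concern holds. The stated 7.7% and 81.6% are not the operating characteristics of the Table 1 rule at any look schedule that the plan allows.

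- Targeted schedules: level 3.3% to 5.4%, power 76.7% to 79.2%. The 80% goal is missed on all nine, taking 33% as printed.
- With the footnoted look at 7: level 3.3% to 5.6%, power 76.7% to 80.2%.
- Chance of declaring safe a combination with a 33% DLT rate: 100 − 79.2 = 20.8% to 100 − 76.7 = 23.3% on the targeted schedules, and 19.8% at best with the look at 7. The stated power implies 100 − 81.6 = 18.4%.

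The true significance level is lower than stated and within the 10% goal. The error therefore lies in overstated power and a misdescribed design, not in an excess of false stops.

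**What to change.** In the Table 1 footnote and in Section 10.2.1, replace the two figures with: *depending on look timing, a 1-sided significance level of 3.3% to 5.6% and 77% to 80% power at a 33% DLT rate*. Add that the 80% power goal is only approximately met. SAP 3.2.1 then inherits the correction by its reference.

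If 7.7% and 81.6% are kept as properties of a parent boundary, name that boundary and its look times, and print the Table 1 values beside them.

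In the CSR, report the exact level and power for the look sizes actually used.

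The cost is wording only. The stated power becomes slightly less favourable and the stated significance level lower. The stopping limits, the looks and the number of subjects do not change.

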3.1.1.2 Definition of DLT in Phase 1b

All toxicities will be graded using the CTCAE version 4.0 (Appendix A).

The occurrence of any of the following toxicities during DLT evaluation period (ie, 6-week period from the initial administration of talimogene laherparepvec and

pembrolizumab in combination) will be considered a DLT, if judged by the investigator to be related to the administration of talimogene laherparepvec and/or pembrolizumab:

- Grade 4 non-hematologic (non-laboratory) toxicity
- Grade 3 or higher pneumonitis
- Grade 3 non-hematologic (non-laboratory) toxicity lasting > 3 days despite optimal supportive care
- Grade 3 fatigue will not be classified as DLT, irrespective of duration
- Any grade 3 or higher non-hematologic laboratory value if:
 - medical intervention is required, or
 - the abnormality leads to hospitalization, or
 - the abnormality persists at grade 3 or higher for >1 week unless deemed not clinically important per both investigator and sponsor
- Grade 3 or grade 4 febrile neutropenia
- Thrombocytopenia < 25 x 10⁹/L associated with bleeding event requiring intervention
- Serious herpetic event:
 - Herpetic encephalitis, encephalomyelitis, or disseminated herpetic infection
- Grade 5 toxicity (ie, death)
- Any other intolerable toxicity leading to permanent discontinuation of talimogene laherparepvec or pembrolizumab

If a subject experiences a DLT during the DLT evaluation period, study treatments will be discontinued for that subject.

An expansion cohort of up to 22 treated subjects will be enrolled so there will be approximately 40 treated subjects in total to estimate the efficacy of the combination of talimogene laherparepvec with pembrolizumab.

3.1.2 Phase 3 Study Design

Phase 3 is a multicenter, placebo-controlled, double-blind, randomized trial to evaluate the efficacy, as assessed by OS, of treatment with talimogene laherparepvec with pembrolizumab versus placebo with pembrolizumab in subjects with recurrent or metastatic SCCHN. Approximately 450 subjects will be randomized 1:1 to receive the following:

- Arm 1: talimogene laherparepvec plus pembrolizumab
- Arm 2: placebo plus pembrolizumab

Randomization will be stratified by HPV status at baseline (HPV- negative versus HPV-positive) and ECOG performance status (0 versus 1).

3.1.3 Tumor Assessment

3.1.3.1 Eligibility Assessment

Phase 1b

Conventional RECIST v1.1 ([Eisenhauer et al, 2009](#)), with the following modification, will be used by the investigator to determine eligibility:

- Increased total target lesions to a maximum of 10 (up to a maximum of 5 per organ)

Phase 3

Conventional RECIST v1.1 ([Eisenhauer et al, 2009](#)) with no modifications will be used by the investigator to determine eligibility.

3.1.3.2 Response Assessment

For both phase 1b and phase 3, a variation of RECIST v1.1, irRECIST, will be used by the investigator to assess tumor response and make treatment decisions, and to assess the secondary tumor response related endpoints in the phase 1b and phase 3 portions of the study. In addition, for phase 3 only, investigators will also be asked to determine and document tumor responses per standard RECIST v1.1, although treatment decisions should NOT be made based on RECIST v1.1. Details for irRECIST can be found in [Appendix D](#), and details for RECIST v1.1 can be found in [Appendix E](#).

Radiographic tumor assessments will be performed independent of treatment cycle at week 9 (± 1 week), week 18 (± 1 week), and then every 9 weeks (± 1 week) or more frequently if clinically indicated until confirmed progressive disease per irRECIST (iPD) or start of a new anticancer treatment. Radiographic tumor assessments should not be adjusted for cycle initiation delays and performed according to the calendar.

Radiographic tumor imaging assessment at screening (baseline) (computed tomography [CT] scan, positron emission tomography [PET]/contrast enhanced CT scan, or magnetic resonance imaging [MRI]) must include the neck, chest, abdomen and all other sites of disease. A CT scan or MRI of the brain should only be performed if signs or symptoms suggestive of central nervous system [CNS] metastases are present. The imaging modality selected (eg, CT or MRI) should remain constant for any individual subject.

3.1.4 Follow-up

3.1.4.1 Safety Follow-up

All subjects who receive investigational product will complete a safety follow-up visit approximately 30 (+7) days after the last dose of study treatment. Adverse events and

disease related events will be collected as described in [Section 9.2](#). Serious adverse events and any concomitant medications associated with serious adverse events observed by the investigators or reported by the subjects that occur through 90 (+7) days after the cessation of all study treatment or 30 (+7) days following cessation of treatment if the subject initiates new anticancer therapy, whichever is earlier, will be reported to Amgen and recorded in the CRF.

3.1.4.2 Long-term Follow-up

After the safety follow-up visit, all subjects will enter the long-term follow-up. Subjects will be followed for survival and subsequent anticancer therapies every 12 weeks (± 28 days) from safety follow-up for approximately 36 months after the last subject is enrolled. In addition, talimogene laherparepvec/placebo related adverse events that occur through the end of the long-term follow-up will be reported.

For subjects who discontinue study treatment without documented iPD and have not initiated a new anticancer therapy, every effort should be made to continue monitoring tumor response status by clinical and radiographic tumor assessments, and to complete PRO questionnaires as described in [Section 7.7](#).

3.2 Number of Sites

The study will be conducted at approximately 140 sites in Australia, Europe, North America, Latin America, Asia, and other regions. Additional sites and countries may be added. Sites that do not enroll subjects within approximately 4 months of site initiation may be closed.

3.3 Number of Subjects

Participants in this clinical investigation shall be referred to as “subjects”.

Approximately 490 subjects will be enrolled in this study: approximately 40 subjects will be enrolled in phase 1b and approximately 450 subjects will be enrolled in phase 3 Global Full Analysis Set (FAS[G]). Refer to [Section 10.2](#) for sample size considerations.

3.4 Replacement of Subjects

Subjects enrolled in phase 1b may be replaced if they are not evaluable for DLT (eg, a subject did not receive study treatment, or ended the study treatment before completion of DLT evaluation period for a reason other than experiencing a DLT).

Subjects enrolled in phase 3 who are withdrawn or removed from treatment or from the study will not be replaced.

3.5 Estimated Study Duration

3.5.1 Study Duration for Subjects

The duration of screening for each subject will be approximately 28 days. The duration of treatment will vary for each subject. Subjects enrolled (phase 1b)/randomized (phase 3) have an estimated median treatment period of 7 months, but can be treated for up to 24 months. All subjects will complete a safety follow-up visit approximately 30 (+7) days after the last dose of study treatment. After the safety follow-up visit subjects will enter the long-term follow-up. During this period, subjects will be followed for survival for approximately 36 months after the last subject is **enrolled**. The study duration for an individual subject is expected to be 45 months. The actual duration of the study for an individual subject may vary depending upon the time required to reach the study specified number of OS events.

3.5.2 End of Study

Primary Completion: The primary completion date is defined as the date when the last subject is assessed or receives an intervention for the final collection of data for the primary endpoint(s), for the purposes of conducting the primary analysis, whether the study concluded as planned in the protocol or was terminated early.

If a study concludes prior to the primary completion date originally planned in the protocol (ie, early termination of the study), then the primary completion will be the date when the last subject is assessed or receives an intervention for evaluation in the study (ie, last subject last visit).

Primary Completion Phase 1b only: The time when the last phase 1b subject is assessed or receives an intervention for the purposes of final collection of data for the primary efficacy endpoint of phase 1b. The primary completion is anticipated to occur when the last phase 1b subject completes the week 9 tumor response assessment.

End of Study (end of trial): The end of study date is defined as the date when the last subject **across all sites** is assessed or receives an intervention for evaluation in the study (ie, last subject last visit), following any additional parts in the study (eg, long-term follow-up), as applicable. This is anticipated to occur 36 months after the last subject is enrolled.

4. SUBJECT ELIGIBILITY

Investigators will be expected to maintain a screening log of all potential study candidates that includes limited information about the potential candidate (eg, date of screening).

Before any study-specific activities/procedure, the appropriate written informed consent must be obtained (see [Section 11.1](#)).

4.1 Inclusion Criteria

- 101 Subject has provided informed consent prior to initiation of any study-specific activities/procedures
- 102 Male or female age ≥ 18 years at the time of informed consent
- 103 Histologically confirmed diagnosis of metastatic or recurrent SCCHN of the oral cavity, oropharynx, hypopharynx, or larynx. Disease must be unsuitable for curative surgical resection and must not be amenable to curative radiotherapy.
- 104 Disease must have progressed after treatment with a platinum-containing regimen and should be defined as one of the following:
- disease progression or recurrence between 3 to 6 months of prior curatively intended multimodal therapy (which includes platinum therapy) for locoregionally advanced SCCHN.

Note: This criterion is only applicable for subjects who have not had treatment in the recurrent/metastatic setting.

- disease progression or recurrence after prior platinum therapy in the recurrent or metastatic setting
- 105 Subject must be candidate for intralesional therapy administration defined as one or more of the following:
- at least 1 injectable cutaneous, subcutaneous, or nodal SCCHN tumor ≥ 10 mm in longest diameter
 - multiple injectable cutaneous, subcutaneous, or nodal SCCHN tumors that in aggregate have a longest diameter of ≥ 10 mm

Note: Mucosal surfaces of tumor lesions and visceral metastases should not be injected.

- 106 Subject must have radiographically measurable disease per RECIST v1.1 ([Eisenhauer et al, 2009](#)). Target lesions must not be chosen from a previously irradiated field unless there has been radiographically and/or pathologically documented tumor progression in that lesion prior to enrollment
- 107 ECOG performance status of 0 or 1

108 Adequate organ function determined prior to enrollment, defined as follows:

- Hematological
 - $ANC \geq 1.5 \times 10^9/L$
 - platelet count $\geq 100 \times 10^9/L$
 - hemoglobin ≥ 9 g/dL

Note: Subjects who have received transfusion of blood products (including platelets or red blood cells, or administration of colony stimulating factors [including G-CSF, GM-CSF, or recombinant erythropoietin) within 4 weeks prior to the first study treatment will be excluded.

- Renal
 - serum creatinine ≤ 1.5 x upper limit of normal (ULN), OR creatinine clearance ≥ 60 mL/min for a subject with creatinine levels > 1.5 x ULN. (Note: Creatinine clearance need not be determined if the baseline serum creatinine is within normal limits. Creatinine clearance should be determined per institutional standard).
- Hepatic
 - total bilirubin ≤ 1.5 x ULN OR direct bilirubin \leq ULN for a subject with total bilirubin level > 1.5 x ULN
 - aspartate aminotransferase (AST) ≤ 2.5 x ULN OR ≤ 5 x ULN for a subject with liver metastases
 - alanine aminotransferase (ALT) ≤ 2.5 x ULN OR ≤ 5 x ULN for a subject with liver metastases
- Coagulation
 - international normalization ratio (INR) or prothrombin time (PT) ≤ 1.5 x ULN, unless the subject is receiving anticoagulant therapy, in which case PT and partial thromboplastin time (PTT)/activated PTT (aPTT) must be within therapeutic range of intended use of anticoagulants
 - PTT or aPTT ≤ 1.5 x ULN unless the subject is receiving anticoagulant therapy as long as PT and PTT/aPTT is within therapeutic range of intended use of anticoagulants

109 Female subject of childbearing potential must have a negative pregnancy test within 72 hours prior to enrollment. If urine pregnancy test is positive or cannot be confirmed as negative, a serum pregnancy test will be required.

110 Phase 1b: Subject has a formalin fixed paraffin-embedded tumor sample from the primary or metastatic lesion that must be submitted within 4 weeks of enrollment for PD-L1, HPV-testing of oropharyngeal cancer (if not performed locally) and biomarker analyses.

Phase 3: Subject has a formalin fixed paraffin embedded tumor sample that is adequate for PD-L1 assessment prior to randomization (sites will be blinded to PD-L1 analysis). Tumor tissue from the subject must be submitted to a central laboratory during screening. Refer to the laboratory manual for more detailed tissue collection procedures.

111 Phase 3: Have results from local testing of HPV of tumor specimen for oropharyngeal cancer defined as p16 IHC testing using the CINtec® assay and a 70% cutoff point. If the assay is unavailable locally, sites must submit archived or recently biopsied formalin-fixed paraffin-embedded tumor tissue (block or unstained tumor slides) from either the primary or metastatic lesion for central laboratory testing. Note: HPV stratification in this trial will be performed using local or central testing of HPV status in subjects with oropharynx cancer. Oral cavity, hypopharynx, and larynx cancer are not required to undergo HPV testing by p16 IHC as by convention, they are assumed to be HPV negative. Please note that results from local testing of HPV of tumor specimen for oropharyngeal cancer patients are required for both phases of the study. Performing p16-IHC testing using the CINtec® assay is only required for phase 3.

